9.3. Recording and Follow-Up of Adverse Events and/or Serious Adverse Events

Adverse Event and Serious Adverse Event Recording

- An AE/SAE that begins or worsens after informed consent is signed should be recorded on the Adverse Event Form in the eCRF. Conditions that were present at the time informed consent was given should be recorded on the Medical History Form in the eCRF.
- When an AE/SAE occurs, it is the responsibility of the investigator to review all documentation (eg, hospital progress notes, laboratory reports, and diagnostics reports) related to the event.
- The investigator (or delegate) will then record all relevant AE/SAE information in the eCRF.
- It is **not** acceptable for the investigator to send photocopies of the participant's medical records in lieu of completing the AE eCRF page.
- There may be instances when copies of medical records for certain cases are requested. In this case, all participant identifiers, with the exception of the participant number, will be redacted on the copies of the medical records before submission.
- The investigator will attempt to establish a diagnosis of the event based on signs, symptoms, and/or other clinical information. Whenever possible, the diagnosis (not the individual signs/symptoms) will be documented as the AE/SAE. When a clear diagnosis cannot be identified, each sign or symptom should be reported as a separate AE/SAE.

To the extent possible, each AE/SAE should be evaluated to determine:

- The severity grade (CTCAE Grade 1 to 5). See below for further instructions on the assessment of intensity.
- Whether there is at least a reasonable possibility that the AE is related to the study treatment (including itacitinib(s) and/or reference therapy): suspected (yes) or not suspected (no). See below for further instructions on the assessment of causality.
- The start and end dates, unless unresolved at final follow-up.
- The action taken with regard to study treatment as a result of the AE/SAE(s) and/or reference therapy.
- The event outcome (eg, not recovered/not resolved, recovered/resolved, recovering/resolving, recovered/resolved with sequelae, fatal, unknown).
- The seriousness, as per the SAE definition provided in Section 9.2.

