3.4. Sample Size Considerations

Part 1 is a single-arm open-label study. The sample size calculation is based on the primary endpoint of \geq Grade 2 CRS rate by Day 14. It was considered that $60\% \geq$ Grade 2 CRS by Day 14 is clinically relevant in this setting. Based on a target rate of 60%, a sample size of 62 will provide 90% power to exclude a higher limit of 79% of a 2-sided 95% CI. The sample size calculation is based on an EAS (see Section [5.3](#) for definition).

[Table 2](#) represents CRS rates and CIs for a sample size of 62.

Table 2: Cytokine Release Syndrome Rates and 95% Confidence Intervals

Sample Size	Number of CRS	CRS Rate (%)	95% CI (%)
62	36	58.1	44.8, 70.5
62	38	61.3	48.1, 73.4
62	40	64.5	51.3, 76.3
62	42	67.7	54.7, 79.1
62	44	71.0	58.1, 81.8

Part 2 is a randomized expansion of the study; itacitinib 200 mg BID versus placebo.

As in Part 1, the primary endpoint is Grade \geq 2 CRS rate by Day 14. Assuming Grade \geq 2 CRS rate in the placebo arm is 50% ([Nastoupil et al 2020](#)) and is 20% in the treatment arm (~30%

change in CRS rate), a sample size of 23 evaluable participants per group would provide 70% power based on a 1-sided Type I error rate of 5%. Sufficient number of participants will be enrolled to yield 23 evaluable participants in each group.

A Bayesian interpretation for the selection and impact of the sample size can be provided in terms posterior probabilities. As the response rate based on CRS rate has a binomial (n, p) distribution with s number of responders out of n participants, it is common to use a conjugate Beta (a, b) prior which leads to a Beta($a + s$, $b + n - s$) posterior distribution. For this exercise, we assume a noninformative Beta(1,1) (\sim Uniform(0,1) prior).

Table 3 presents scenarios of Bayesian posterior probability of demonstrating a treatment difference ($\geq 30\%$) by Day 14 in CRS rates, between the itacitinib 200 mg BID group and the placebo group, under various CRS rates assumption (number and percentage of participants experiencing \geq Grade 2 CRS).

Table 3: Bayesian Posterior Probability of Demonstrating a Treatment Difference

N^a (%) 200 BID Group	N^b (%) Placebo	Posterior Probability^c
2 (8.7)	9 (39.1)	43.7
	12 (52.5)	79.4
	14 (60.9)	93.4
5 (21.7)	9 (39.1)	13.9
	12 (52.5)	45.9
	14 (60.9)	67.9
7 (30.4)	9 (39.1)	4.7
	12 (52.5)	22.7
	14 (60.9)	44.7

^a Number of participants with CRS \geq Grade 2, out of 23 participants, in the 200 mg BID group.

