5.3. Analysis Populations

Table 4 presents the populations for analysis.

Table 4: Analysis Populations

Population	Description
Safety population	The safety population includes all enrolled participants who received at least 1 dose of study drug. All safety analyses will be conducted using the safety population.
Efficacy evaluable analysis set (EAS)	The EAS includes all participants who have received at least 1 dose of study drug and have received IEC therapy. All efficacy analyses will be conducted using EAS.

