6.5. Study Drug Compliance

Overall compliance (%) for itacitinib will be calculated for all participants as follows:

$$\text{Overall compliance (relative dose intensity) (\%)} = 100\% \times (\text{total dose administered}) / (\text{intended dose})$$

Intended dose is defined as the sum of the doses prescribed by the investigator accounting both for planned dose reductions as well as those reductions or increases mandated by the investigator.

For IEC infusions, compliance calculations are not applicable. Infusion information collected in eCRF may be listed as needed, including any temporary infusion interruption.

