9.2. Adverse Events

9.2.1. Adverse Event Definitions

A TEAE is any AE either reported for the first time or worsening of a pre-existing event after the first dose of study drug. Analysis of AEs (as discussed below) will be limited to TEAEs, but data listings will include all AEs regardless of their timing in relation to study drug administration.

Adverse events will be tabulated by MedDRA PT and SOC. Severity of AEs will be graded using the NCI CTCAE v5.0. The CTCAE reporting guidelines and grading details are available on the Cancer Therapy Evaluation Program website.

The subset of AEs considered by the investigator to be related to study drug will be considered to be treatment-related AEs. If the investigator does not specify the relationship of the AE to study drug, the AE will be considered to be treatment-related. The incidence of AEs and treatment-related AEs will be tabulated.

In addition, serious TEAEs will also be tabulated.

Any missing onset date, causality, or severity must be queried for resolution. Unresolved missing causality and severity will be handled according to the following rules:

- An unresolved missing causality will be considered treatment-related.
- An unresolved missing severity will be identified as an unknown severity.

For purposes of analysis, all AEs will be considered TEAEs unless the AE can unequivocally be defined as not treatment-emergent.

- If the stop/resolution date is before the first dose administration date on Day 1, then the AE will be considered as not being treatment-emergent.
- If both the month and day are missing, and the last day of the year is before the first dose administration date on Day 1, then the AE will not be considered treatment-emergent.

- If only the day is missing, and the last day of the month is before the first dose administration date on Day 1, then the AE will not be considered treatment-emergent.
- If only the day is missing, and the first day of the month is after the first dose administration date on Day 1, then the AE will be considered treatment-emergent.

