9.2.2. Adverse Event Summaries

An overall summary of AEs by treatment group will include the following:

- Number (%) of participants who had any TEAEs
- Number (%) of participants who had any serious TEAEs
- Number (%) of participants who had any Grade 3 or higher TEAEs
- Number (%) of participants who had any TEAEs related to study drug
- Number (%) of participants who had any serious TEAEs related to study drug
- Number (%) of participants who had any Grade 3 or higher TEAEs related to study drug
- Number (%) of participants who temporarily interrupted study drug because of TEAEs
- Number (%) of participants who permanently discontinued study drug because of TEAEs
- Number (%) of participants who had study drug dose reductions because of TEAEs
- Number (%) of participants who had a fatal TEAE
- Number (%) of participants who had any AEs related to IEC therapy

The following summaries will be produced by MedDRA term (if 10 or fewer participants appear in a table, a listing may be appropriate):

- Summary of TEAEs by SOC and PT
- Summary of TEAEs by PT in decreasing order of frequency
- Summary of TEAEs by SOC, PT, and maximum severity
- Summary of \geq Grade 3 TEAEs by SOC and PT
- Summary of \geq Grade 3 TEAEs by PT in decreasing order of frequency
- Summary of \geq Grade 3 TEAEs by SOC, PT, and maximum severity
- Summary of serious TEAEs by SOC and PT
- Summary of serious TEAEs by PT in decreasing order of frequency
- Summary of study drug treatment-related TEAEs by SOC and PT
- Summary of study drug treatment-related TEAEs by SOC, PT, and maximum severity

- Summary of IEC therapy treatment-related TEAEs by SOC and PT
- Summary of IEC therapy treatment-related TEAEs by SOC, PT, and maximum severity
- Summary of treatment-related \geq Grade 3 study drug TEAEs by SOC and PT
- Summary of treatment-related \geq Grade 3 IEC therapy TEAEs by SOC and PT
- Summary of study drug treatment-related serious TEAEs by SOC and PT
- Summary of IEC therapy treatment-related serious TEAEs by SOC and PT
- Summary of TEAEs with a fatal outcome by SOC and PT
- Summary of TEAEs leading to study drug dose interruptions by SOC and PT
- Summary of TEAEs leading to IEC therapy interruptions by SOC and PT
- Summary of TEAEs leading to study drug dose reduction by SOC and PT
- Summary of TEAEs leading to withdrawal of study drug
- Summary of Deaths

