1.1 Disposition		
1.1.1	Analysis Populations	Enrolled
1.1.2	Summary of Participant Disposition	Safety
1.1.3	Summary of Number of Participants Enrolled by Site	Enrolled
1.1.4	Summary of Protocol Deviations	Safety

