Table No.	Title	Population
3.2.20.1	Summary of Treatment-Emergent Adverse Events Leading to IEC Therapy Interruption by MedDRA System Organ Class and Preferred Term	Safety
3.2.21.1	Summary of Treatment-Emergent Adverse Events Leading to Study Drug Dose Reduction by MedDRA System Organ Class and Preferred Term	Safety
3.2.22.1	Summary of Treatment-Emergent Adverse Events Leading to Withdrawal of Study Drug	Safety

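### No by-arm summary identifies adverse events that delay or cancel the cell infusion, and Part 2 participants dosed but never infused leave the primary analysis with no sensitivity analysis to restore them

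*SAP*

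**What the plan says.** **Timing.** Under the Protocol Summary, study drug starts on Day -3 and the cells are given on Day 0. SAP 4.1.3 places the first dose 3 days to 1 day before the infusion.

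**Adverse events.** SAP 9.2.1 counts events from first dosing: "A TEAE is any AE either reported for the first time or worsening of a pre-existing event after the first dose of study drug". They are summarised by treatment group in the safety population, which requires a dose of study drug but no infusion (SAP 5.3, 9.1). One bullet in SAP 9.2.2 concerns an action on the cell therapy: "Summary of TEAEs leading to IEC therapy interruptions by SOC and PT". Appendix A repeats it as Table 3.2.20.1: "Summary of Treatment-Emergent Adverse Events Leading to IEC Therapy Interruption by MedDRA System Organ Class and Preferred Term". The overall AE summary has rows for interruption, discontinuation and reduction of study drug, and none for an action on the cells.

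**Disposition and exposure.** SAP 6.2 and Table 1.1.2 ("Summary of Participant Disposition") cover study drug discontinuation and study withdrawal with reasons, in the safety population. SAP 6.4 puts exposure to cell therapy on the safety population too, but Appendix A puts Table 3.1.2 (exposure to cell therapy) on the EAS.

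**Efficacy set.** SAP 5.3: "The EAS includes all participants who have received at least 1 dose of study drug and have received IEC therapy". SAP 7.1 runs every Part 2 efficacy analysis on it, and Protocol 10.4.1.2 does the same for the primary. On numbers, SAP 3.4 says: "Sufficient number of participants will be enrolled to yield 23 evaluable participants in each group".

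**Missing data.** The rule in SAP 7.2.1.1 and the sensitivity analysis in 7.2.1.2 both deal with dropout after the infusion and before Day 14.

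**The concern.** For a prophylactic given ahead of a potentially curative cell therapy, an important possible harm is that the patient gets the cells late or not at all. Protocol 2.4 names infection and myelosuppression as risks of itacitinib. The plan should be able to show, by arm, whether such events held up or stopped the infusion.

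There is also a question of comparability. Receiving the cells happens after randomisation and after dosing, and study drug could affect it. Restricting the primary to infused participants can therefore bias the Part 2 comparison if non-infusion differs by arm. Enrolment runs until 23 per arm are evaluable, so the primary denominators would look complete whatever was lost beforehand.

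**Working it through.** **1. Which planned outputs could show a delayed or cancelled infusion?**

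- Table 3.2.20.1: interruption only. Where SAP 6.5 uses the word for the cells, it means a break in an infusion under way: "Infusion information collected in eCRF may be listed as needed, including any temporary infusion interruption". On that reading, an infusion that never began is not counted.
- General TEAE tables: they contain the event by arm, but not its consequence for the infusion.
- Table 1.1.1 (analysis populations): gives the difference in counts between the safety population and the EAS, with no reason planned.
- Table 1.1.2: no infused or not-infused row is specified.
- Table 3.1.2: on the EAS, so by definition it has no participants without an infusion. On the safety population, as SAP 6.4 says, it could show them.
- Listing 2.7.4: events leading to a change in study drug only.

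None links an event to delay or non-administration.

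**2. Who leaves the primary?** Someone infused late has had both study drug and cells and stays in the EAS. Someone dosed and never infused leaves it. The 7.2.1.2 sensitivity analysis removes further participants and restores none.

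**3. The plan's own power figure.** Inputs from SAP 3.4: 23 per arm, 50% versus 20%, one-sided 5%. Using the pooled Z form of SAP 7.2.1:

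- SE under the null = sqrt(0.35 × 0.65 × 2/23) = 0.1407
- SE under the alternative = sqrt((0.25 + 0.16)/23) = 0.1335
- Power = Φ[(0.30 − 1.645 × 0.1407)/0.1335] = 69.6%, which agrees with the stated 70%.

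**4. Illustration.** The documents give no Part 2 non-infusion rate, so the counts below are assumptions. The test is z = (pA − pB)/sqrt[p(1 − p)(1/n1 + 1/n2)], with p the pooled rate. The starting point is 5/23 versus 12/23: p = 17/46 = 0.370, z = −0.304/0.1423 = −2.138, one-sided p-value 0.016.

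Add k never-infused itacitinib participants and none on placebo:

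| k | Counted as non-events | p | Counted as events | p |
|---|---|---|---|---|
| 1 | 5/24 vs 12/23 | 0.013 | 6/24 vs 12/23 | 0.028 |
| 2 | 5/25 vs 12/23 | 0.010 | 7/25 vs 12/23 | 0.044 |
| 3 | 5/26 vs 12/23 | 0.008 | 8/26 vs 12/23 | 0.064 |
| 4 | 5/27 vs 12/23 | 0.006 | 9/27 vs 12/23 | 0.089 |

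Less one-sided losses, counted as events: 3 versus 1 gives 8/26 vs 13/24, p = 0.047; 3 versus 3 gives 8/26 vs 15/26, z = −1.955, p = 0.025.

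**The case against.** A reader might infer that toxicity delaying or cancelling the infusion appears in no by-arm table at all. The documents do not support that. An event between first dose and infusion is a TEAE, and it is tabulated by arm among all events and, where it applies, among those that are Grade 3 or higher, serious, drug-related, or leading to study drug interruption or withdrawal. Only its link to the infusion is missing.

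Nor do the documents show that Table 3.2.20.1 would read zero. Protocol 9.3 records "The action taken with regard to study treatment as a result of the AE/SAE(s) and/or reference therapy", but the response options are not shown, so a held infusion might be coded as an interruption.

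The example is also a hard case. It takes strongly one-sided loss to carry the p-value past 0.05. The endpoint is CRS after cell therapy, which a never-infused participant cannot have. Counted as non-events, losses confined to the itacitinib arm make the result stronger, so the EAS is then the more cautious set. The 0.064 belongs to a different outcome, CRS or not infused. Investigators and participants are blinded in Part 2, which limits differential decisions to withhold the cells, though not differential toxicity.

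On frequency, Protocol 2.3.3 reports 26 enrolled at the Part 1 interim, all of whom had completed Day 14. Enrolment is at Day -3, so this suggests no pre-infusion loss. It was the once-daily dose, however, and the exact 95% upper limit for 0/26 is 13% (1 − 0.025^(1/26)).

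These points stand, and they limit the size of the concern. They do not supply the missing link or the missing analysis.

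**Conclusion.** The point holds in two parts. First, no planned by-arm summary identifies TEAEs that delay or cancel the cell infusion. Second, Part 2 participants dosed but never infused are outside the primary, and no sensitivity analysis restores them.

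A reader might go further and infer that delayed participants are also lost, or that the Part 2 result is likely to reverse. Neither follows: late infusion keeps a participant in the EAS, and the documents give no sign of how often non-infusion will occur at the twice-daily dose. The p-value range of 0.008 to 0.064 rests on an assumed 5/23 versus 12/23 and on three losses all in one arm. It shows that a handful of cases could matter with 23 per arm, not that they will occur.

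This is an inexpensive improvement to the analysis plan. It is not a reason to change the primary analysis set or the sample size.

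**What to change.** 1. **AE summary.** Widen the SAP 9.2.2 bullet and Table 3.2.20.1 to TEAEs leading to delay, interruption or non-administration of the cell therapy, by arm on the safety population. A listing will do if there are few cases, as 9.2.2 already allows. First check that the action-taken field in the CRF can separate these outcomes.
2. **Exposure and disposition.** Reconcile SAP 6.4 (safety population) with Table 3.1.2 (EAS), so that the table shows by arm how many dosed participants were and were not infused. Add counts of randomised, dosed and infused participants to Part 2 disposition, with reasons for non-infusion where collected.
3. **Supplementary estimate.** Keep the EAS as primary. Add the Part 2 rate difference and 95% CI in all randomised participants, counting never-infused participants once as non-events and once as events. Label the second as a composite of CRS or not infused.

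The cost is SAP wording, a few table changes and one extra analysis run two ways. The reported range may be wider. Reasons for non-infusion may need a CRF check, because the documents do not show that they are captured.

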9.3. Eastern Cooperative Oncology Group Performance Status

ECOG performance status at scheduled assessment times are summarized by treatment group and in overall population. The changes in ECOG status from the baseline may also be summarized.

9.4. Clinical Laboratory Tests

9.4.1. Laboratory Value Definitions

Laboratory values and change from baseline values will be summarized descriptively by visit. Baseline will be determined according to [Table 5](#). If there are multiple values that meet the criteria for baseline, [Table 5](#) may be referred to as tiebreaker to delineate which value will be defined as baseline.

Table 5: Baseline Laboratory Identification

Priority	Laboratory Visit	Proximity to Visit Window	Tiebreaker
1	Scheduled	In-window	Use smallest laboratory sequence number
2	Unscheduled	In-window	
3	Scheduled	Out-of-window	

Laboratory test values outside the normal range will be assessed for severity based on CTCAE grade or similar criteria where clinical intervention is required for CTCAE grading. The incidence of abnormal laboratory values and shift tables relative to baseline will be tabulated.

9.4.2. Laboratory Value Summaries

All test results and associated normal ranges from laboratories will be reported in SI units. Any laboratory test results and associated normal ranges from local laboratories will be converted to

SI units. For test results that will be summarized with available normal ranges, the number and percentage of participants with the laboratory values being low (but never high), normal, high (but never low), and both low and high will be calculated for each test. This shift summary may be produced for each test for the safety population. The denominator for the percentage calculation will use the number of participants in the baseline category (ie, low, high, normal, missing) as the denominator for the percentage in each of the categories during the treatment period. For numeric laboratory values, baseline value, postbaseline value, change from baseline, and percentage change from baseline will be summarized by visit.

Shift tables will be presented showing change in CTC grade from baseline to worst postbaseline grade. Separate summaries for abnormally high and abnormally low laboratory values will be provided when the laboratory parameter has both high and low grading criteria. The denominator for the percentage calculation will be the number of participants in the baseline category.

The following summaries will be produced for laboratory data (by laboratory parameter) reported on treatment. All laboratory assessments will be listed, and those collected later than 30 days after the last treatment/exposure date will be flagged in the listings.

- Number and percentage of participants with worst postbaseline CTC grade (regardless of the baseline status) will be summarized. Each participant will be counted only for the worst grade observed after baseline.
- Shift tables using CTC grades comparing baseline with the worst postbaseline value will be produced for hematology, chemistry, and some other laboratory parameters with CTC grades.
- For laboratory parameters where CTC grades are not defined, shift tables to the worst postbaseline value will be produced using the low/normal/high classifications based on laboratory reference ranges.
- Number and percentage of participants meeting categorical liver function test criteria, including ALT, AST, and ALT or AST ($\geq 3 \times$, $5 \times$, $8 \times$, $10 \times$, $20 \times$ ULN); total bilirubin ($\geq 1 \times$, $2 \times$ ULN); ALP ($\geq 1.5 \times$, $2 \times$, $3 \times$, $5 \times$, $8 \times$, $10 \times$ ULN); combined categories of ALT/AST and total bilirubin (eg, ALT/AST $\geq 3 \times$ ULN and total bilirubin \geq ULN); combined categories of ALT/AST total bilirubin; and ALP (ALT or AST $\geq 3 \times$ ULN and total bilirubin $\geq 2 \times$ ULN and ALP $< 2 \times$ ULN at the same visit; potential drug induced liver injury). The worst values observed postbaseline for each participant will be used for each of the categories.

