11. Participants who are currently breastfeeding.

12. Receipt of a prior investigational study agent within 4 weeks before screening visit.

Note: Participants who have received anti-CD19 IEC therapy on a study where cell infusion occurred greater than 4 weeks before the screening visit are NOT excluded.

13. Any condition that would, in the investigator's judgment, interfere with full participation in the study, including administration of itacitinib and attending required study visits (if outpatient); pose a significant risk to the participant; or interfere with interpretation of study data.

14. Inability of the participant to swallow and retain oral medication.

15. Participants with laboratory values at screening defined in [Table 8](#).

Table 8: Exclusionary Laboratory Values

Laboratory Parameter		Exclusion Criterion
Hematology		
a	Platelets	$\leq 10 \times 10^9/L$
b	Hemoglobin	$\leq 8 \text{ g/dL}$
Hepatic		
e	ALT	$\geq 2.5 \times \text{ULN}$ for age, $> 5 \times \text{ULN}$ in the presence of liver metastases
f	AST	$\geq 2.5 \times \text{ULN}$ for age, $> 5 \times \text{ULN}$ in the presence of liver metastases
g	Total bilirubin	$> 1.5 \times \text{ULN}$ or $> 3 \times \text{ULN}$ in the presence of documented Gilbert's syndrome (unconjugated hyperbilirubinemia)
Renal		
h	Creatinine clearance	
Participants ≥ 18 years of age: $\leq 50 \text{ mL/minute}$ based on Cockcroft-Gault formula.
 
Participants < 18 years of age: GFR < 15 based on revised Schwartz formula 2009.
 
The cutoffs for mild, moderate, and severe renal insufficiency based on Cockcroft-Gault are 60-90 mL/min, 30-59 mL/min, and 0-29 mL/min, respectively.
 
Note: Creatinine clearance necessitates a 24-hour urine sample before the blood draw to calculate. An estimated value is acceptable.

Cardiopulmonary		
i	Cardiac LVEF	$\leq 40\%$ confirmed by ECHO/multigated analysis
j	Adequate pulmonary function	$\geq \text{Grade 2 dyspnea}$ and $\geq \text{Grade 2 hypoxia}$

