APPENDIX D. MANAGEMENT OF POTENTIAL HY'S LAW CASES

INTRODUCTION

During the course of the study, the investigator will remain vigilant for increases in liver biochemistry. The investigator is responsible for determining whether a participant meets potential Hy's law (PHL) criteria at any point during the study.

The investigator participates, in conjunction with Incyte clinical project and pharmacovigilance representatives, in the review and assessment of cases fulfilling PHL criteria to ascertain whether there is an alternative explanation for the elevations in liver biochemistry other than drug-induced liver injury caused by the study treatment.

The investigator fulfills requirements for the recording of data pertaining to PHL or Hy's law cases and AE/SAE reporting according to the outcome of the review and assessment in line with standard safety reporting processes.

DEFINITIONS

For the purpose of this process definitions are as follows

Potential Hy's Law

An increase in AST or ALT $> 3 \times$ ULN and total bilirubin $> 2 \times$ ULN at any point during the study. The elevations do not have to be at the same time or within a specified timeframe.

Hy's Law

An increase in AST or ALT $> 3 \times$ ULN and total bilirubin $> 2 \times$ ULN, where no other reason can be found to explain the combination of increases, eg, elevated serum ALP indicating cholestasis, viral hepatitis, another drug.

ACTIONS REQUIRED IN CASES OF AST OR ALT $> 3 \times$ ULN OR TOTAL BILIRUBIN $\geq 2 \times$ ULN

Identification and Determination of Potential Hy's Law

To identify cases of AST or ALT $> 3 \times$ ULN or total bilirubin $> 2 \times$ ULN and consequently determine whether the participant meets PHL criteria, please follow the instructions below:

- Review the laboratory report and if a participant has AST or ALT $> 3 \times$ ULN OR total bilirubin $> 2 \times$ ULN at any visit:
 - Determine without delay whether the participant meets PHL criteria by reviewing laboratory reports from all previous visits.
 - Enter the laboratory data into the laboratory eCRF as soon as possible.

Potential Hy's Law Criteria Not Met

If the participant has NOT had AST or ALT $> 3 \times$ ULN AND total bilirubin $> 2 \times$ ULN at any point in the study (the elevations do not have to be at the same time or within a specified timeframe), irrespective of ALP, please follow the instruction below:

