- Perform follow-up on subsequent laboratory results according to the guidance provided in Section 6.1.3 of the Protocol.

Potential Hy's Law Criteria Met

If the participant has had AST or ALT $> 3 \times$ ULN AND total bilirubin $> 2 \times$ ULN at any point in the study (the elevations do not have to be at the same time or within a specified timeframe), irrespective of ALP, please follow the instruction below:

- Have participant discontinue study treatment.
- Notify Incyte study team without delay.
 - The investigator, or designee, should contact the medical monitor to discuss and agree upon an approach for the study participant's follow-up and the continuous review of data.
- Monitor the participant until liver biochemistry parameters and appropriate clinical symptoms and signs return to normal or baseline levels, or as medically indicated.
- Investigate the etiology of the event and perform any relevant diagnostic investigations as discussed with the medical monitor.
- Enter the laboratory data into the laboratory CRF as soon as possible.
- If at any time (in consultation with the medical monitor) the PHL case meets serious criteria, report it as an SAE using standard reporting procedures.

REVIEW AND ASSESSMENT

No later than 3 weeks after the biochemistry abnormality was initially detected and the criteria for PHL was met, the medical monitor, Incyte pharmacovigilance physician, and investigator will discuss and review available data and agree on whether there is an alternative explanation for the elevations in liver biochemistry other than drug-induced liver injury caused by the study treatment. Participant matter experts will be included in the review as appropriate.

Evaluation of Alternative Causes

In order to gather additional clinical information to seek other possible causes of the observed liver test abnormalities, the following alternative etiologies should be considered, including, but not limited to,

- Active viral hepatitis
- Alcoholic and autoimmune hepatitis

- Hepatobiliary disorders
 - Biliary tract disease, such as migration of gallstones or intrahepatic lesions, more often causes cholestatic injury initially and should be investigated with gall bladder and ductal imaging studies, especially if alkaline phosphatase is increased. Malignant interruption of the biliary tract also should be considered.
- Concomitant treatment

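### Liver elevations allowed at entry are not separated from new ones: Table 8 exceptions can pre-fill one component of potential Hy's law, and the SAP's combined liver rows have no baseline split

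*SAP*

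**What the plan says.** **Entry limits (Protocol 5.2, Table 8).** ALT or AST at or above 2.5 × ULN excludes, but with liver metastases only values above 5 × ULN do. Total bilirubin above 1.5 × ULN excludes, but the limit is 3 × ULN "in the presence of documented Gilbert's syndrome (unconjugated hyperbilirubinemia").

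**Potential Hy's law (Protocol Appendix D).** The definition is "An increase in AST or ALT $> 3 \times$ ULN and total bilirubin $> 2 \times$ ULN at any point during the study". On timing: "The elevations do not have to be at the same time or within a specified timeframe". Once either analyte crosses its limit, the site must look back: "Determine without delay whether the participant meets PHL criteria by reviewing laboratory reports from all previous visits". If both components are met, the first instruction is: "Have participant discontinue study treatment". Joint review follows within three weeks. If another explanation is agreed, treatment resumes; if not, discontinuation is permanent. Hy's law proper applies only "where no other reason can be found to explain the combination of increases".

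**Liver table (SAP 9.4.2; Table 3.3.6 in SAP Appendix A).** Participants are counted against fixed multiples of ULN: ALT/AST from 3 × upward, bilirubin from 1 × and 2 ×, and ALT/AST with bilirubin combined. One combined row also requires ALP below 2 × ULN at the same visit and is labelled as potential drug-induced liver injury. The rule for all rows is: "The worst values observed postbaseline for each participant will be used for each of the categories". SAP 4.1.5 sets baseline for safety as the last value before first study drug.

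**The concern.** Table 8 deliberately accepts some participants whose liver values already exceed a threshold used later. Neither Appendix D nor the SAP liver table says what happens to those values. Two things follow.

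- In the protocol, an accepted entry value can supply part of the criterion that carries the discontinuation instruction and, rarely, all of it.
- In the analysis, an elevation that was present before dosing and simply continues is counted in the same row as one that arose on study drug.

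Liver cases are few and weigh heavily, so misattributing even one matters. In Part 2 one participant is 1/23 = 4.3% of an arm. Part 1 has no control, and Protocol 10.4.3 says the safety summaries for both dose groups and placebo will be used to confirm the choice of dose.

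**Working it through.** The documents give no figure to reproduce on this point. The check compares the highest value Table 8 admits with each later threshold, in the four groups defined by the two exceptions. Values are multiples of ULN.

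| Group | Highest ALT/AST admitted | Highest bilirubin admitted | ALT/AST > 3 at entry? | Bilirubin > 2 at entry? | Potential Hy's law from entry values alone? |
|---|---|---|---|---|---|
| Neither exception | below 2.5 | 1.5 | no | no | no |
| Gilbert's only | below 2.5 | 3 | no | yes | no |
| Liver metastases only | 5 | 1.5 | yes | no | no |
| Both | 5 | 3 | yes | yes | yes |

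Entry values alone complete the criterion in one group of four. In two groups one component can be filled at entry and the other must appear later. In the remaining group neither component can be met at entry.

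**What pre-filling means.** Take liver metastases only, entering at ALT 4 and bilirubin 1.2. Both are admitted (4 ≤ 5; 1.2 ≤ 1.5). Because the components need not coincide and earlier visits are reviewed, any later bilirubin above 2 completes the criterion, even if ALT has since fallen.

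**SAP rows reached if entry values persist after dosing.**

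- Neither exception: bilirubin ≥ 1 only, since 1.5 ≥ 1.
- Gilbert's only: bilirubin ≥ 1 and ≥ 2.
- Liver metastases only: ALT/AST ≥ 3, ALT/AST ≥ 5 (at exactly 5), bilirubin ≥ 1, and the combined row ALT/AST ≥ 3 with bilirubin ≥ ULN. The participant above falls in that combined row with no change at all.
- Both: all of these, plus ALT/AST ≥ 3 with bilirubin ≥ 2 at the same visit if ALP is below 2.

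**Which outputs already use baseline.** SAP 9.4.2 and Appendix A plan change from baseline by visit, chemistry shifts by low/normal/high (Table 3.3.2.2) and by CTC grade (Table 3.3.3.2), and treatment-emergent worsening in chemistry (Table 3.3.3.5). All work analyte by analyte. None covers a combined row.

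**Scale, by assumption only.** The documents give no prevalences. Suppose 5–40% have liver involvement, 3–10% have Gilbert's syndrome, and the two are independent.

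- Share with both: 0.05 × 0.03 = 0.0015 to 0.40 × 0.10 = 0.04, that is 0.15–4%.
- Part 2, both arms: 46 × 0.0015 = 0.07 to 46 × 0.04 = 1.8 participants.
- Part 1: 62 × 0.0015 = 0.09 to 62 × 0.04 = 2.5 participants.

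These are ceilings within the assumed range, because not everyone in the group would exceed both thresholds. More participants qualify for a single exception, but the share of them above a threshold is unknown. Any rate within the groups would need invented distributions of entry values, so none is given.

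**The case against.** The case against has several parts, and much of it stands.

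- **Entry values are not counted in the SAP table.** This stands. The rows use postbaseline values, so a participant entering at bilirubin 1.2 × ULN reaches a row only if a later value does. The issue is persistence.
- **Ordinary entrants are unaffected by the Hy's law question.** This stands. Without an exception, neither component can be met at entry.
- **Potential Hy's law is a screen, not a diagnosis.** This stands. Review looks for other causes, and documented Gilbert's syndrome or liver involvement could be accepted as one. But the discontinuation instruction comes first, review may take three weeks of a 30-day treatment period, and nothing says whether pre-dose values count. The only test of change covers repeat episodes whose earlier cause was chronic or progressing malignant disease.
- **The definition speaks of an increase, which could mean a rise.** This is weak. The steps that identify and act on cases use absolute multiples of ULN only.
- **Planned tables already use baseline.** This largely stands for single analytes, including bilirubin from 1 × ULN. It fails for the combined rows, which a reader would have to rebuild from the liver chemistry listing (2.8.10).
- **Randomisation balances pre-existing elevations.** It does so only in expectation. With 23 per arm a chance imbalance of one or two is possible, and Part 1 has no comparator.

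**Conclusion.** The gap is real but narrow. Table 8 lets one component of potential Hy's law be met at entry under a single exception, and both only when liver metastases and Gilbert's syndrome coexist. Appendix D does not set pre-dose values aside. The SAP liver table does not separate persisting from new elevations, and this matters most for the combined ALT/AST–bilirubin rows, one of which is reachable from entry values with liver metastases alone.

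A reader might infer more: that entry values by themselves create a liver case and stop treatment for anyone admitted under an exception, or that the liver signal in Part 2 is likely to be distorted. The documents do not support that. One exception is not enough to complete the criterion, the SAP needs a value after dosing, review can end in resumption, and the number of participants concerned is not stated and is probably small. The comparison of limits rests on the text alone; the scale figures rest on assumed prevalences and independence. This is a cheap improvement to safety reporting plus a request for clarification. It does not touch the primary analysis.

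**What to change.** **SAP 9.4.2 and Table 3.3.6.** Keep the planned counts. Show each liver category, including every combined row, split by whether the SAP 4.1.5 baseline already met that category. For participants whose baseline did, show baseline and worst postbaseline values. For a combined row, the flag is set when baseline meets all of its conditions.

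The cost is one derived flag and one extra row per category; no new data are collected and no planned count is lost. The split does not remove participants who start just below a threshold and cross it through ordinary variation. Those remain counted as new and can be inspected in the liver chemistry listing.

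**Protocol.** Table 8 and Appendix D must be reconciled, and the sponsor should state how values present before dosing are treated under the potential Hy's law criteria. This needs a protocol clarification. How the clinical rule should come out is for the sponsor, and none is proposed here. When doing so, it is worth noting that Appendix D uses strict inequalities at any time, whereas the SAP's potential drug-induced liver injury row uses ≥, the same visit and an ALP condition, so the two counts will not match.
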